5.7 Expected Duration of Trial

The end of the trial will be defined as last patient last visit; each individual subject will remain on the trial until they have completed all five visits and have had the final follow up phone call.

6 Trial Procedures and assessments

6.1 By Visit

Pre-Screening

The pre-screening procedure will involve reviewing notes and undertaking telephone interviews with the patients to evaluate whether they are suitable and interested in taking part in the study.

Screening

If the subject appears to be suitable and is interested in taking part in the study they will be provided with a patient information leaflet before they are invited to the clinic where they will have the opportunity to ask any questions or discuss the information leaflet with the Investigator or the study team. The investigator or a suitably qualified person designated by the investigator will obtain written informed consent from each subject or the subject's legally acceptable representative before any study-specific activity is performed. The investigator will retain the original of each subject's signed consent form, which will be stored in the Centre of neuroimaging sciences (CNS) in a locked cabinet and a copy will be provided to the patient.

Following provision of informed consent, the subject will have a medical screening, physical and psychiatric examinations including completion of the NPI, MoCA and SAPS-PD, familiarisation, and tolerability check in the mock MRI scanner (to see how well participants can tolerate the scanner environment) and basic training on the visual processing tasks. Blood and urine samples will be taken for safety tests, drug screen and pregnancy testing (if applicable).

Day 1- Baseline visit

Patients will attend the clinic on the morning of study day 1. They will be checked to make sure that they continue to meet all inclusion criteria and none of the exclusion criteria and undergo physical and neurological examinations, including completion of the NPI, MoCA, SAPS-PD, PDQ and EQ. To build the patient profile at the start of the

study, baseline questionnaire and assessments will be carried out. These include the Non-motor symptoms, SCOPA-MOTOR, PD sleepiness, WTAR, verbal fluency, months' reversed, clinical impression of severity index and the NEVHI (assessments described in section 6.2). The recall period for each of the assessments will be adapted to when the visit is taking place. Following completion of the baseline assessments the participant will receive their first dose of study medication. Saracatinib/placebo will be administered followed by a 3 hour stay during which vitals will be assessed at regular intervals. A physical examination will take place prior to discharge. On discharge, medication will be provided to be taken for the following 12 days, confirmed by daily telephone contact.

Days 2 to 13

Patients will take a dose (two 50mg tablets) of study medication at home each morning. The study team will telephone the patient/their carer each day to confirm the medication has been taken and to assess for any adverse events.

Day 14 Scanning visit

On the 14th day participants will be asked to attend the research facility in the time window of 12-16 days after their first dose, given their last dose of the study medication and then at approximately 2 hours post dose will be scanned using BOLD fMRI whilst doing the Kanizsa task and the Meppelink task. After MRI scanning is complete participants will have mismatch negativity measured using EEG. They will also have the NPI, SAPD-PD, PD sleepiness scale, NEVHI, PDQ and EQ (details of the tasks and scans outlined in section 6.2 below).

Following this, participants will undergo a physical examination and assessment by the study physician, and they will also have blood sampling for pharmacokinetic/drug exposure levels. Participants will then be discharged provided there are no concerns. There will then be a minimum 14-day washout (+/- 2 days), after which they will return for day 1 of the second study period. All study procedures (apart from the profiling assessments) on days 1 through 14 will be repeated for study period 2.

Participants will be contacted by telephone between 10 and 14 days after their final visit to check for adverse events.

Early termination visit

If a participant decides to stop the study treatment they will be given a phone call by a study physician and may be invited for an early termination visit where participants will return any unused medication undergo a physical and neurological examination, vitals, and an ECG.

6.2 Assessments

6.2.1 Profiling assessments

North-East Visual Hallucinations Interview (NEVHI)

The NEVHI is a visual complaints questionnaire that is used to assess the phenomenology of visual hallucinations (Urwylter et al., 2014). The participants will be given the NEVHI at the baseline visit to understand their hallucinations.

Wechsler Test of Adult Reading (WTAR)

The WTAR was developed to predict intellectual performance in adults and had shown to have a significant correlation with measures for intellectual functioning. It consists of 50 words with irregular 'grapheme to phoneme translation' which the participant must read out loud (Whitney et al., 2010). The WTAR takes approximately 90 seconds to complete.

Non-motor symptoms questionnaire

A nine-domain questionnaire consisting of 30 questions designed to test the frequency and severity of the non-motor symptoms of Parkinson's disease over the past month (Chaudhuri and Martinez-Martin, 2008). This questionnaire will take approximately 5 minutes to complete.

SCOPA-MOTOR scale

A 21-question test on the severity of motor symptoms PD. The test consists of three components; evaluation of motor symptoms (10 items), activities of daily living (ADL 7 items) and motor complications (4 items). All items are scored from 0 (normal) to 3 (severe) on the questionnaire (Martinez-Martin et al., 2008). This will take approximately 10 minutes to complete.

Parkinson's disease sleepiness scale

The PDSS is a 15-item scale for the assessment of sleep disorders in Parkinson's disease over the past week. The PDSS involves patients marking their response to each item on a 10cm long visual analogue scale that goes from 0 (worst) to 10 (best). All of the items of the scale are focused on nocturnal sleep except item 15 which is about daytime sleepiness. The total score on the PDSS is the sum of all of the items with a maximum score of 150 (Martinez-Martin et al., 2008).

Cognitive assessment

A brief cognitive assessment consisting of two parts; Months reversed (saying the months of the year backwards from December in 90 seconds) and Lexical fluency (giving the

patient 1 minute to name as many words as they can beginning with a particular letter) (Dubois et al., 2007).

Clinical impression of severity index

An assessment for the clinical severity of motor symptoms in 4 domains: motor signs, disability, motor complication and cognitive status. Each are is scored from 0 (normal) to 6 (very severe) and the global index from 0-24 points (Martinez-Martin et al., 2008).

The Questionnaire for Impulsive-Compulsive Disorders in Parkinson's Disease– Rating Scale (QUIP-RS)

The QUIP-RS (Weintraub et al., 2012) is a self-report measure designed to assess the presence and the severity (on a scale from 0 to 4) of symptoms of impulse control disorders (compulsive gambling, buying, sexual behavior, and eating) and related disorders (including hobbyism, punning, and dopamine dysregulation syndrome). The questionnaire takes approximately 5 minutes to complete.

6.2.2 Study Assessments

Neuropsychiatric Inventory (NPI)

The NPI is an informant-based scale that was developed to assess neuropsychiatric symptoms. It consists of 12 items, but section A and B are delusions and hallucinations respectively. If symptoms are present, then more information is obtained through questions about frequency (scale of 1-3) and severity (scale of 1-4). The total scores are added up to get the NPI total score (Ferreira et al., 2015). An inclusion criterion for this is included in section 5.1.

Montreal Cognitive Assessment (MoCA)

The MoCA is a one-page 30-point test administered in 10 minutes. The MoCA focuses on different aspects of cognitive abilities by testing various areas such as short-term memory recall, visuospatial abilities, multiple aspects of executive functions such as attention, concentration, working memory and Language. The final questions test orientation to time and place (Nasreddine et al., 2005). Please see section 5.1 for the minimum cut off score for inclusion in this study.

Scale for the Assessment of Positive Symptoms- Parkinson's Disease (SAPS-PD)

The Scale for the Assessment of Positive Symptoms (SAPS) was originally designed for use in schizophrenia and was found to be a reliable tool for people with Parkinson's disease (Fernandez et al., 2008). Therefore, the SAPS-PD comprises of the 9 items that were found to be most frequently reported in patients with PD psychosis. It comprises of questions about hallucinations and delusions and the severity of the symptoms (Voss et al., 2013).

EEG

MMN is an ERP evoked in response to unattended changes in background stimulation. MMN is believed to reflect an automatic process of detecting a mismatch between a deviant stimulus and a sensory-memory trace. Smaller amplitudes of MMN have been consistently identified in schizophrenia subjects, showing promise as a quantitative clinical biomarker of the disease. MMN amplitude is associated with ketamine-induced psychotic experiences. MMN has demonstrated stability in clinical populations with high test-retest reliability over 1 year. Hence, MMN represents a potentially informative probe of sensory processes relevant to hallucinations/psychosis for use in experimental medicine studies of novel therapeutics. The MMN test takes approximately 10 minutes with 25 minutes set up time. Further details will be provided in the study manual.

MRI scan

The scanning protocol will comprise a localiser to ensure a good positioning in the scanner, T1-weighted structural scan (to allow registration to a template), multi-echo resting state scan (for connectivity), Kanizsa illusion, the Meppelink task and a perfusion scan using pseudo-continuous ASL (to determine changes in neurovascular coupling caused by the drug).

Kanizsa Illusion

The Kanizsa task is a task that comprises of illusory contours which are perceived edges that 'bridge gaps between aligned luminance edges' but do not exist physically. The Kanizsa task is a task that used the perceived edges to give a direct comparison of the physiological response to illusory contours which may reveal information about object perception (Mendola et al., 1999). This task will take approximately 12 minutes.

Visual pop-out task (Meppelink task)

A visual task where objects, animals and people appear out of noise and participants must press a button when they recognise what it is. A previous study by Meppelink et. Al. reported that patients with visual hallucinations and Parkinson's disease had decreased activation of the lateral occipital cortex several seconds before image recognition compared to patients with PD but no psychosis and healthy controls (Meppelink et al., 2009). This task consists of 50 images appearing from noise and each video lasts for 30 seconds. In total, the task will take approximately 20 minutes.

Visual analogue scales of physical fatigue, mental fatigue and overall health

Visual scales ranging from 0-100 where the patient marks on the scale how they would rate their physical fatigue, mental fatigue, and overall health today.

PDQ

The Parkinson’s disease questionnaire is a quality of life questionnaire specific to Parkinson’s disease (Young et al., 2013). It is composed of 39 questions and participants are asked to read a statement and indicate on a scale of ‘Never’ to ‘Always or cannot do at all’ which applies best. The questionnaire assesses difficulties of daily living across 8 dimensions. The scale can provide a single figure that can be used to assess the overall quality of life related to health.

EQ-5D

The European quality of life 5-dimension questionnaire is a standardized questionnaire for measuring health-related quality of life in 5 dimensions; mobility, self-care, usual activities, pain/discomfort, and anxiety/depression. Each dimension has 3 statements and participants are asked to tick which statement best describes their health today.

6.3 Laboratory Tests

PK and plasma exposure levels will be measured on days 1 and 14 (pre and post scanning) at approximately the same time of day to control for any bioanalytical timing effects.

Haematology

Haematology will consist of the following tests:

Erythrocytes (red blood cells)	Haemoglobin
Haematocrit	Platelets
Leukocytes (white blood cells [WBCs]) with absolute differential	

Urinalysis

Urinalysis will consist of the following tests:

Protein	Glucose
Blood	Nitrite

Urine microscopy will be performed if urinalysis is abnormal. Microscopy consists of red blood cell/high-power field, white blood cell/high-power field, and casts.

Chemistry

Chemistry evaluations will consist of the following standard chemistry panel:

Albumin	Alkaline phosphatase
ALT	AST
Blood urea nitrogen	Calcium
Carbon dioxide	Chloride
Creatinine	Glucose
Gamma-glutamyl transferase	Sodium
Potassium	Bilirubin (total), if above ULN total bilirubin will be fractionated
Protein (total)	

Diagnostic Screening

Serum

Serum diagnostic evaluations will include the following tests:

Hepatitis Screen (hepatitis A virus antibody, HBsAg, HCV antibody)
FSH, LH (females of NCBP aged under 50 only)

Urine

A urine drug screen will include the following tests:

Amphetamines	3,4-methylenedioxy-methamphetamine
Barbiturates	Methadone / Metabolite
Benzodiazepines	Opiates
Buprenorphine / Metabolite	Cocaine / Metabolites
Cannabinoids	Phencyclidine

7 Assessment of Efficacy

This study is not powered for clinical efficacy, it is powered for proof of concept and mechanism of action (change in visual cortex fMRI signal). We nonetheless record symptoms and exploratory analyses will be conducted with these. In addition, we will

explore relationships between the neuroimaging and EEG endpoints and symptoms. The symptom scores will be:

- Factor summary score on the Scale for the Assessment of Positive Symptoms in Parkinson's disease (SAPS-PD)
- Factor summary score on the Neuropsychiatric Inventory (NPI)

8 Assessment of Safety

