3.3 Trial Flowchart

Study days	Screening	Study period 1 and 2 ¹												Early termination visit ²
		Day 1- Baseline and Placebo/drug dose					Day 2-13	Day 14- Scanning and assessment day					Follow up	
		Hours						Hours						
	Pre-Dose	0	1	2	3		Pre-Dose	0	1	2	3	4		
Patient consent	X													
Physical examination	X	X						X					X	X
Neurological examination	X	X						X					X	X
Vitals ³	X	X		X	X	X		X					X	X
12- lead ECG	X	X						X						X
Oral dose of drug ⁴			X				X		X					
NPI ⁵	X	X						X						
MoCA	X	X						X						
SAPS-PD	X	X						X						
Lab safety blood and urine tests ⁶	X	X											X	
Hepatitis screen	X													
Urine drug screen	X	X						X						
Pharmacokinetic blood sample ⁷		X						X			X	X		
Non-motor symptoms ⁸		X												
SCOPA-MOTOR ⁷		X												
PD sleepiness scale ⁷		X						X						

¹ There will be a minimum 14-day washout period between study periods

² This visit will only take place if a participant decides to discontinue study treatment

³ Vitals will consist of semi recumbent blood pressure, heart rate, temperature, and respiratory rate.

⁴ 100mg of Saracatinib or placebo

⁵ To ensure that the inclusion criteria have been met. Minimum combined score of 6 in hallucinations and delusions section.

⁶ For females of child-bearing potential.

⁷ To measure the levels of Saracatinib/Placebo in the blood at baseline and scanning day.

⁸ Profiling assessments- only applicable to period one.

PROTOCOL SCRIPT

Word reading (WTAR) ⁷		X														
Verbal fluency ⁸		X														
Months reversed ⁹		X														
NEVHI ⁸		X						X								
Clinical impression of severity index ⁸		X														
fMRI											X					
EEG												X				
Kanizsa illusion ¹⁰											X					
Meppelink task (visual pop-out) ⁹											X					
Visual Analogue scales								X								
PDQ		X											X			
EQ		X											X			
Dispense study medication						X										
Telephone call							X							X		X
Adverse event monitoring																

⁹ Profiling assessments- only applicable to period one

¹⁰ While in the MRI scanner.

4 Trial Medication

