5.2 Exclusion Criteria

The subject must be excluded from participating in the study if the subject:

1. Is a female of child bearing potential
2. Is currently taking anticholinergic medication
3. Is currently taking any medication known to be a moderate or potent CYP3A4 inducer or inhibitor.
4. Has an ongoing disability, medical or neurological history, cognitive impairment, or conditions that in the opinion of the investigator may interfere with study conduct or clinical assessments.
5. Refuses to be withdrawn from quetiapine (see section 4.7).
6. Has a family history of psychosis in a first degree relative
7. Has poor peripheral arterial/venous access or recent wrist trauma that will restrict ability to gain venous access.
8. Is currently using prescription or non-prescription drugs and herbal supplements, which are deemed to affect the integrity of the study, within 7 days or 5 half-lives (whichever is longer) prior to the first dose of trial medication. As an exception, paracetamol or acetaminophen may be used at doses of ≤ 1 g/day.
9. Has a history of sensitivity to any of the study medications or any of the excipient constituents.
10. Has a history of febrile illness within 5 days prior to the first dose
11. Has a hairstyle which would affect EEG recording.
12. Has any condition possibly affecting drug absorption (eg, gastrectomy).
13. Has a history of regular alcohol consumption exceeding 14 units/week (6 glasses of 13.0% wine (175ml), 6 pints of 4.0% lager or ale (568ml), 5 pints of 4.5% cider (568 ml) or 14 glasses of 10.0% spirits (25ml)) within 6 months of screening.
14. Uses tobacco- or nicotine-containing products in excess of the equivalent of 5 cigarettes per day.

15. Uses caffeine containing products of the equivalence of 5 cups of regular filter coffee per day
16. Has a positive urine drug screen on or after the screening visit during their active involvement in the study for opiates, methadone, cocaine, amphetamines (including MDMA), barbiturates, benzodiazepines and cannabinoids.
17. Is unwilling or unable to comply with the Lifestyle guidelines.
18. Has, in the opinion of the investigator, has any medical or psychological condition or social circumstances which would impair their ability to participate reliably in the study, or who may increase the risk to themselves or others by participating.

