19. Is male and is unwilling to follow the contraception guidance or has a female partner of child bearing potential who is unwilling to follow the contraception guidance throughout the study.
20. Serum alanine aminotransferase (ALT) or aspartate aminotransferase (AST) ≥ 2.5 x upper limit of normal (ULN)
21. Total bilirubin ≥ 1.25 x ULN
22. Known congenital long QT syndrome
23. Baseline resting QTcF > 470 ms on 12 lead ECG
24. Positive hepatitis C antibody, hepatitis B virus surface antigen or hepatitis B virus core antibody at screening
25. Known to have tested positive for human immunodeficiency virus.
26. Participation in another clinical study with an investigational product administered in the last 3 months
27. Below the lower limit of normal Hb, total WBC and neutrophils on blood counts as per the reference ranges of the laboratory conducting the tests.

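### Exclusion 24 turns partly on hepatitis B core antibody, but the hepatitis screen in section 6.3 does not list that marker, so the criterion cannot be applied in full from the listed tests

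*Combined protocol and SAP*

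**What the plan says.** The exclusion list in section 5.2 is mandatory: "The subject must be excluded from participating in the study if the subject" meets any item on it. Item 24 reads "Positive hepatitis C antibody, hepatitis B virus surface antigen or hepatitis B virus core antibody at screening".

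Section 6.3, under Diagnostic Screening, introduces the serum panel with "Serum diagnostic evaluations will include the following tests" and then lists "Hepatitis Screen (hepatitis A virus antibody, HBsAg, HCV antibody". The only other serum entry is FSH and LH for certain women.

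The flowchart in section 3.3 has one row, "Hepatitis screen", marked at the screening visit only and without components. The screening-visit text in section 6.1 says "Blood and urine samples will be taken for safety tests, drug screen and pregnancy testing (if applicable") and names no hepatitis marker.

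**The concern.** An exclusion that depends on a laboratory result needs that result to be on the panel. Sections 5.5.1 and 9.2 allow randomisation only once every selection criterion is met, and the Day 1 text in section 6.1 has staff re-check all the criteria before the first dose. If the panel is run as listed, staff have no core-antibody result to check.

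Two things are at stake. A subject who is positive for core antibody alone could pass every listed test and be dosed, although the protocol says that such a subject is excluded. And for every subject, a monitor asking for evidence on this part of exclusion 24 would find none in the planned data.

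**Working it through.** No arithmetic applies beyond counting; the check sets the two lists side by side.

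| Marker | Exclusion 24 (section 5.2) | Hepatitis screen (section 6.3) |
|---|---|---|
| HCV antibody | yes | yes |
| HBsAg | yes | yes |
| Hepatitis B core antibody | yes | **no** |
| Hepatitis A antibody | no | yes |

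Of the three exclusion markers, two have a listed test and one (3 − 2 = 1) does not.

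**Is core antibody ordered elsewhere?** The flowchart row gives no components. The screening-visit text is generic. The haematology, urinalysis and chemistry lists in section 6.3 contain no hepatitis marker. Core antibody appears only in exclusion 24.

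**Could medical history supply it?** The wording points the other way. Exclusion 24 is tied to a positive result at screening. Its neighbours use different language where history is enough: exclusion 25 concerns a known positive HIV test, and exclusion 22 a known congenital long QT syndrome.

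**Is section 6.3 generally loose about matching its exclusions?** The urine drug screen is a useful comparison because it has the same kind of lead-in. Exclusion 16 names opiates, methadone, cocaine, amphetamines including MDMA, barbiturates, benzodiazepines and cannabinoids. All of these are on the urine list, which also adds buprenorphine and phencyclidine. So the urine panel covers everything its exclusion needs, and more; the hepatitis panel falls one short.

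**Is the gap an artefact of the text?** Both entries read as complete, with no blackout or break at either place.

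**The case against.** The best defence is that the serum list is not closed. Section 6.3 says that haematology, urinalysis and chemistry consist of their tests, whereas serum diagnostics include theirs. A site could add core antibody, and exclusion 24 itself gives an investigator reason to obtain it. This stands to the extent that one cannot say the marker will never be measured. It does not remove the mismatch: the parenthesis spells out what the hepatitis screen contains, and nothing in the protocol provides for the extra test.

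It can also be said that other safeguards limit the exposure. Exclusions 20 and 21 set limits on ALT, AST and bilirubin. Inclusion 6 requires good health on history and laboratory tests. Exclusions 4 and 18 leave room for investigator judgement. That is fair on the size of the risk, but these are separate criteria and none gives a core-antibody result.

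Three stronger readings are tempting, and the documents do not support them.

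- A reader might infer that exclusion 24 is unworkable as a whole. It is not: the HCV antibody and HBsAg parts can be applied from the listed screen.
- A reader might infer that ineligible subjects will be enrolled. The documents support only that they could be. No frequency of isolated core-antibody positivity is given, and the number wrongly enrolled may be zero.
- A reader might see a second error in hepatitis A antibody being tested with no matching exclusion. Testing beyond the listed exclusions is ordinary here, as buprenorphine and phencyclidine show, and inclusion 6 lets laboratory results inform the investigator's judgement.

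**Conclusion.** Wrong as written, and minor. Two stated rules disagree: a mandatory safety exclusion relies on three markers, and the screen meant to serve it lists two of them. The gap is one marker of three. The approximately 30 enrolled subjects are the number for whom that part of the criterion would be undocumented; it is not an estimate of how many would be wrongly enrolled.

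This rests on two assumptions: that sites run the hepatitis screen as listed, and that no operational document outside the supplied text adds the missing marker. The sample size, power, error rates, randomisation and primary fMRI analysis are unaffected.

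**What to change.** Reconcile exclusion 24 in section 5.2 with the hepatitis screen in section 6.3, so that every marker named in the criterion has a listed test. Which marker set is right is a clinical decision for the sponsor, and this review takes no position on it. Once it is settled, naming the components against the flowchart row in section 3.3 would keep the three places aligned.

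The cost is a wording change or a small change to the screening panel, depending on the sponsor's decision. No statistical section needs to change.
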